8.2.3 Other Analyses

Statistical analysis on blood pressure will be done on safety analysis set.

For Blood Pressure (SBP, DBP),

- Descriptive summary statistics (number of subjects (n), mean, standard deviation (SD), median, minimum and maximum) of blood pressure at before and after administration will be summarized.
- The change of after administration compared before administration for blood pressure will be analyzed using paired t-test.

In addition to the above summaries and analyses, the following Basic Results Tables will also be produced for the final study report.:

- Baseline Characteristics in safety analysis set
- Summary of Baseline Characteristics in safety analysis set
- All Adverse Events in safety analysis set
- Summary of Each SOC/PT of Adverse Events in safety analysis set
- Summary of Effectiveness Evaluation in effectiveness analysis set
- Subjects Flow Chart(the number of subjects who started the study, the number of subjects who completed the study)

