7. RESEARCH METHODS

7.1. Study Design

This study is open-label, non-comparative, observational, non-interventional, prospective and multi-center study in which subjects are administered PRISTIQ® as part of routine practice at Korean health care centers by accredited psychiatrists. The observation period for each subject is from initiating administration of PRISTIQ® until week 8. If administration is discontinued before week 8, observation should be done for at least 28 days from the last administration day. There will be no visit or activity mandated by this study and routine observation will be done during the above-mentioned period.

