7.3.3.1. Long-term use study

As PRISTIQ® could be used in a long time considering its indication, data from the patients administered in a long time out of enrolled patients will be collected and analyzed separately. Safety and effectiveness data of at least 60 subjects who have been administered PRISTIQ® over 6 months out of enrolled subjects will be collected.

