7.4.7. Blood Pressure

If the physician performed blood pressure check for diagnostics or monitoring in usual medical practice, check 'done' and record the results. If there is any clinically significant abnormal result in blood pressure during or after administration compared to one before administration, please check 'yes' and record the abnormality in "9. Safety evaluation" clause.

- Date of blood pressure check (before / during / after)
- Results (sBP / dBp)

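### SAP 8.2.3 analyses blood pressure only before versus after administration and does not define 'after', so the 'during' readings that the protocol records have no planned summary or test

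*SAP*

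**What the plan says.** Protocol 7.4.7 has the CRF capture systolic and diastolic pressure against three labels: "Date of blood pressure check (before / during / after". Readings exist only where routine care produced them: "If the physician performed blood pressure check for diagnostics or monitoring in usual medical practice". The investigator flags "any clinically significant abnormal result in blood pressure during or after administration compared to one before administration" and enters it in the safety evaluation. In that sentence, as in the CRF field, 'during' and 'after' are separate alternatives.

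SAP 8.2.3 works on the safety analysis set. It says that descriptive statistics "of blood pressure at before and after administration will be summarized", and then: "The change of after administration compared before administration for blood pressure will be analyzed using paired t-test". It names no output for 'during' readings, gives no definition of 'after', and has no rule for a subject who has not stopped the drug. SAP 7 (missing values) is marked not applicable.

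On timing, protocol 7.1 states: "The observation period for each subject is from initiating administration of PRISTIQ® until week 8". It adds: "If administration is discontinued before week 8, observation should be done for at least 28 days from the last administration day". The same section mandates no visits. Protocol 7.3.3.1 also seeks data on "at least 60 subjects who have been administered PRISTIQ® over 6 months out of enrolled subjects".

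**The concern.** Three categories are recorded and two are analysed. The one left out is the on-treatment category, which bears most directly on whether the drug changes blood pressure while it is being taken. Apart from adverse events, blood pressure is the only safety measurement that the SAP gives its own analysis; SAP 1 shows that it was added in version 2.0.

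A programmer holding a CRF variable coded before/during/after, and a SAP that asks for before and after, would most directly take those two codes. The paired test would then compare pre-treatment pressure with off-drug pressure, and only in subjects who stopped and were measured afterwards. A null result could be read as reassurance about pressure on treatment, although no on-treatment reading had entered the test.

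**Working it through.** The documents contain no sample size, power or precision figure for blood pressure, so there is nothing to reproduce. Protocol 7.7 states that no formal sample size calculation was done. The check is a comparison of the texts, followed by an illustration of scale.

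**1. Recorded against analysed.**

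| Category | Protocol 7.4.7 | SAP 8.2.3 summary | SAP 8.2.3 test |
|---|---|---|---|
| Before | recorded, dated | yes | yes |
| During | recorded, dated | none named | none named |
| After | recorded, dated | yes | yes |

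**2. What each meaning of 'after' does to a subject who has a before value.**

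| Later readings | 'After' as on the CRF | 'After' = after first dose |
|---|---|---|
| An off-drug reading, with or without on-drug ones | in the test, off-drug value used | in the test; which reading counts is unstated |
| Stopped, on-drug reading only | out | in |
| Still on drug when data end, on-drug reading only | out | in |

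Under the CRF meaning, 'during' values go unused even in subjects who later stop. Under the other meaning nobody is lost, but the SAP would still have to say which of several readings is the 'after' value.

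**3. Are continuing subjects expected?** Yes. Protocol 7.4.9.2 provides for evaluation at about 8 weeks in patients still taking the drug. SAP 8.2.1.1 has a substitution rule for exposure when medication continues at study completion. No matching rule exists for blood pressure.

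**4. What the test would estimate.** Let d be the mean change on drug and f the fraction of it that remains off drug. With 'after' as on the CRF, the test targets f × d; the on-treatment comparison targets d. Neither value is in the documents. As an assumption only, take d = 3 mmHg and the same d in those who stop and those who continue. Then f = 0, 0.5 and 1 give 0, 1.5 and 3 mmHg, so the test could show all of the on-drug change or none of it.

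**5. Precision, all inputs assumed.** Take 300 subjects with a before and some later reading, and an SD of change of 12 mmHg (range 10 to 15). Half-width = t(0.975, n−1) × SD/√n. For example, n = 150 and SD 12 give 1.976 × 12/√150 = 1.976 × 0.980 = 1.94 mmHg.

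| Share with no 'after' reading | Paired n | SD 10 | SD 12 | SD 15 |
|---|---|---|---|---|
| 0% | 300 | 1.14 | 1.36 | 1.70 |
| 10% | 300 × 0.90 = 270 | 1.20 | 1.44 | 1.80 |
| 50% | 300 × 0.50 = 150 | 1.61 | 1.94 | 2.42 |
| 75% | 300 × 0.25 = 75 | 2.30 | 2.76 | 3.45 |

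The loss of precision is modest unless most pairs are lost. The main issue is which subjects and which period the test describes (step 4).

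**The case against.** The strongest reply is that 'before and after' in a two-level summary can be ordinary pre/post wording, with 'after' meaning any time after treatment began. On-treatment readings would then be eligible and no continuing subject would be lost. The SAP does not rule this out. The protocol's three-way split makes the CRF meaning the more natural one but does not prove it. This objection stands as a limit: the consequence is conditional, and the missing definition is the part that is certain.

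Second, nothing clinically important is concealed. Flagged abnormalities during or after treatment go to the safety evaluation and from there to the adverse event tables of SAP 8.2.1. The 8.2.3 summary also reports n, with means taken over the subjects measured, so a shortfall of 'after' readings would be visible. Both points stand. They lower the stakes but give the on-treatment readings no summary.

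Third, a reader might infer that the 'after' values would come mainly from early stoppers, because protocol 7.1 sets an off-drug window only for those who stop before week 8. The documents do not support that. Subjects who finish treatment at or after week 8 can also have an 'after' reading, and protocol 7.4.7 puts no week-8 limit on blood pressure capture. Protocol 7.3.3.1 collects safety data beyond 6 months. Protocol 9.2 can be read as placing at least 28 post-drug days inside observation generally, although it schedules no blood pressure check.

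Fourth, the analysis is supplementary: SAP 6.1 names adverse event occurrence as the only safety endpoint, and SAP 4 marks hypotheses as not applicable. That is also true, and it is why this is an improvement and not a correction of an error.

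**Conclusion.** The mismatch is established by the text: three blood pressure categories are recorded, two are analysed, and 'after' is undefined. If 'after' carries the protocol's meaning, on-treatment readings are neither summarised nor tested. Subjects with no post-treatment reading then leave the only paired blood pressure test, which describes pressure off drug. If it means after the first dose, the gap closes, but the SAP should say so and name the reading to be used.

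The number of subjects affected cannot be derived from the documents. It is tempting to take 60/600 = 10% as a minimum share still on drug at week 8. It is not a lower bound, because protocol 7.7 allows 600 or more patients, and being on drug at week 8 does not mean that a subject never has an 'after' reading. The half-widths and the 3 mmHg example rest wholly on assumed inputs and show scale only.

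No planned result is shown to be wrong. This is a cheap improvement to a supplementary safety analysis.

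**What to change.** In SAP 8.2.3, keep the before/after summary and paired t-test and add the following:

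- The same descriptive statistics, and the paired change, from the before value to the last on-treatment ('during') reading.
- The n for that comparison, and the median and range of days from first dose to that reading.
- A definition of 'after'. If it was meant as after the first dose, say so and name the last on-treatment reading as the value used for subjects who continue.

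The cost is a few lines of SAP text and one table from data already on the CRF, with no new visits or patients. SAP 3 leaves blood pressure out of the interim analyses, so the table is produced once, for the final report. The drawback is that the last on-treatment reading falls at different times in different subjects, because checks follow routine practice. Reporting the days from first dose makes that visible but does not remove it.

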9 APPENDICES

9.1 APPENDIX 1: NOTES

- Each statistical analysis will be carried out with SAS Software version 9.4 or more recent version.
- Ambiguous data such as “ ≥ 20 ”, “ > 20 ” in ‘Diagnosis Date’, ‘Daily dosage’ variable will be excluded from analysis.
